4.2. EXCLUSION CRITERIA

The following patients are not eligible to join the study:

- 1. Patients undergoing adenoidectomy alone with no tonsillectomy
- Patients with previous oropharyngeal cancer or oral cancer, or any other head and neck cancer such as nasopharyngeal or laryngeal cancer that is currently undergoing or has previously been diagnosed or treated
- 3. Learning disability preventing an adult over 16 years old from giving their own consent

5. SCREENING AND INFORMED CONSENT/ASSENT

Potential patients will be identified from the list of patients having tonsillectomy at the participating hospital by the research nurse. All eligible patients or their parent(s)/ legal guardian(s) (if they under 16 years old), will be contacted by invitation letter before their operation date to inform them of the study. On or before the date of the operation, the patients will have the study explained to them by the research nurse. Children and young people under the age of 16 will also have the study explained to them and their parent(s) or legal guardian(s). If they are willing to participate in the study, they will be asked to give written consent. Parents will give consent and assents will be obtained from young people (aged between 11 and 15 years) in addition to their parent(s) or legal guardian(s) consent.

5.1. INFORMED CONSENT / ASSENT

It is the responsibility of the investigator or research nurse (delegated by the Principal Investigator as captured on the Site Signature and Delegation Log (SSDL)) to obtain written informed consent/assent for each patient prior to performing any study related procedure. Age specific Patient Information Sheets (PIS) are provided to facilitate this process. Investigators must ensure that they adequately explain the aim, anticipated benefits and potential hazards of taking part in the study to the patient, parent(s) or legal guardian(s). The investigator should also stress that the patient, parent(s) or legal guardian(s) are completely free to refuse to take part or withdraw from the study at any time. The patient, parent(s) or legal guardian(s) should be given ample time (e.g. 24 hours) to read the PIS and to discuss their participation with others outside of the site research team. The patient, parent(s) or legal guardian(s) must be given an opportunity to ask questions which should be answered to their satisfaction. The right of the patient, parent(s) or legal guardian(s) to refuse to participate in the study without giving a reason must be respected.

If the patient, parent(s) or legal guardian(s) expresses an interest in participating in the study they should be asked to sign and date the latest version of the Informed Consent Form/Assent Form. The investigator or research nurse must then sign and date the form. A copy of the Informed Consent Form and Assent Form should be given to the patient, their parent(s) or legal guardian(s), a copy should be filed in the hospital notes, and the original placed in the Investigator Site File (ISF). Once the patient is entered into the study the patient's Registration Number (RNO) should be entered on the Informed Consent Form/Assent Form maintained in the ISF. In addition, if the patient, their parent(s) or legal guardian(s) has given explicit consent/assent a copy of the signed Informed Consent Form/Assent Form must be sent in the post to the OROMOUTH Study Office for review.

Details of the informed consent/assent discussions should be recorded in the patient's medical notes, this should include date of, and information regarding, the initial discussion, the date consent/assent was given, with the name of the study and the version number of the PIS and Informed Consent Form/Assent Form. Throughout the study the patient, their parent(s) or legal guardian(s) should have the opportunity to ask questions about the study and any new information that may be relevant to the patient's continued participation should be shared with them in a timely manner. On occasion it may be necessary to re-consent/re-assent the patient in which case the process above should be followed and the patient's right to withdraw from the study respected.

Electronic copies of the PIS and Informed Consent Form/Assent Form are available from the OROMOUTH Study Office and should be printed or photocopied onto the headed paper of the local institution.

Details of all patients approached about the study should be recorded on the Patient Screening/Enrolment Log and with the patient's prior consent/assent their General Practitioner (GP) should also be informed that they are taking part in the study. A GP Letter is provided electronically for this purpose.

6. STUDY ENTRY

Patients should be registered into the study once eligibility is confirmed and informed consent/assent has been obtained. The patients unique RNO will correspond to the ID number of the kit used in the sample collection for that patient. The Registration Form confirming patients' eligibility should be completed and sent to the OROMOUTH Study Office by email or fax using the details below:

Email: [contact]

[contact]

The following details are captured on the Registration Form:

- 1. Name of registering hospital
- 2. Name of investigator
- 3. Patient's initials
- 4. Date of written informed consent
- 5. Confirmation of eligibility criteria

Registration confirmation will be sent from the OROMOUTH Study Office by email to notify the site of the patient's registration on the OROMOUTH database.

7. STUDY PROCEDURES AND SAMPLE COLLECTION

All samples should be collected in accordance to the study procedure manual developed by GSK with details of sample collection kits, volume of samples to be collected and storage temperature requirements.

For a patient to be eligible for inclusion in the data analysis, the following samples are a minimum requirement:

- Oral samples
- Blood
- Oropharyngeal brushings
- Tonsils

 After written consent is obtained, the patients (above 16 years old only) will complete a short study questionnaire including age, gender, history of tobacco/alcohol use, sexual history including age of start of sexual intercourse, lifetime numbers of sexual partners, engagement in oral sex and lifetime number of oral sex partners etc.

- 2. An HPV vaccination history will also be taken. Consent/assent will also be taken from the patient, parent(s) or their guardian(s), if applicable, to obtain the patient's HPV vaccination status from vaccine and medical health records from their GP and/or other relevant health and educational authorities. The data requested will include confirmation of HPV vaccination status, including dates, number of doses and the type of vaccine given.
- 3. Oral fluid samples will be collected for HPV PCR and HPV antibody tests, using an oral rinse and an exudate collection device respectively.
- 4. A 20 30 ml urine sample will be collected for HPV PCR test.
- 5. Blood serum will be taken for HPV and biomarker serology tests. This can be taken after the patient has been anaesthetised if necessary. 20 mls of blood will be taken from patients aged 16 years and above, 10 mls from patients below 16 years old.
- 6. Once the patient is anaesthetised, two brush cytology scrapings using cytobrushes (provided) will be taken: one from the posterior pharynx including above and below the soft palate so that the adenoidal area is included, and a second separate brush scrape will be taken from the back of the tongue (base of tongue).
- 7. Tonsillectomy will then be performed and the tonsillar tissue will be placed in 10% buffered formalin and sent to the pathology department for paraffin embedding according to a specific protocol.
- 8. Stratified sampling will be employed to ensure that sufficient numbers of patients are recruited from all age groups, especially the age groups between 10 and 20 years old.

7.1. PROSPECTIVE LONGITUDINAL SUBSET STUDY

A random selection of around 150 patients will be asked to give oral fluid and urine samples and brushings from their finger tips and under the nails approximately 3 - 6 months after their operation to provide pilot data on persistence and clearance of HPV. These patients may be contacted by phone or letter to arrange an appointment in a clinic or a visit by the researcher at home to obtain the specimens.

7.2. HISTORICAL COMPARISON GROUP

95,000 tonsillectomy samples collected for the National Prospective Tonsillectomy Audit between 2003 -2004 have been archived by the Health Protection Agency (HPA) and now constitute an ethics approved research tissue bank called the National Anonymous Tonsil Archive (REC ref. 08/H0404/54). We will match the patients in our study with a sex and age matched cohort of approximately 1250 anonymised tonsillectomy samples from the above research tissue bank. Tissues from the anonymised tonsillectomy samples will be tested for HPV DNA by PCR and other techniques to provide a historical comparison group of HPV prevalence and distribution. The HPA have confirmed their approval to provide the tonsil samples, provided ethical approval is granted for our study.

If the above is not possible for any logistical reasons, then as an alternative, we may analyse an anonymised sample of up to 650 tonsil samples previously harvested in the PROTECT study in 2000-01, which are currently available to the Chief Investigator. The samples are totally anonymised, and so the only data available is the gender data and whether the age is below or above 9 years of age. These samples have equal numbers of males and females, and the age distribution between older than and younger than 9 years old is equally distributed. Ethics approval has been obtained by the PROTECT study to transfer the samples to our group for use in further ethically-approved studies.

7.3. SAMPLE SHIPMENT

Samples collected from the registered patients, should be sent to the InHANSE laboratory at the University of Birmingham (address below) using the approved courier indicated in the OROMOUTH Sample Collection Instructions.

InHANSE Laboratory

CRC Building School of Cancer Sciences, 3rd Floor University of Birmingham [name], UK

InHANSE will dispatch samples to other laboratories (as appropriate) for testing.

7.4. SAMPLE ANALYSIS

All samples will be analysed using laboratory manuals and standard operating procedures applicable to that organisation.

Table 3: List of laboratories analysing samples

Testing Laboratory	Sample
DDL Diagnostic Laboratory Diagnostic Service Unit [name] The Netherlands	Fresh TonsilsArchive TonsilsOral rinse
Universiteit van Antwerpen Vaxinfectio – CEV [name] [name] Belgium	• Urine
CEVAC Center For Vaccinology UZ GENT - 1BA [name] Belgique	• Serum
InHANSE Laboratory CRC Building School of Cancer Sciences, 3rd Floor, University of Birmingham [name], UK	Nail BrushingsWhite Blood CellsSerum

Testing Laboratory	Sample
GlaxoSmithKline Vaccines Clinical Immunology R & D Department/Building 7 [name] [name] – Belgium	 Oral Mucosal Transudate Urine Fresh Tonsils Archive Tonsils Oropharyngeal brushings

- The oral fluid, nail brushings, oropharyngeal scrapes and urine samples will be tested for HPV DNA by PCR. We may also test them for HPV viral load, viral RNA and p16 RNA. They may also undergo other detection methods, such as in-situ hybridisation (ISH). The oral fluid may also be tested for anti HPV L1 antibodies. Other antibodies e.g. anti E6/7, nucleic acids, other HPV related proteins and total antibodies may also be assayed.
- 2. The tonsil samples will be tested for HPV DNA by PCR. They may also undergo other forms of detection of HPV such as in-situ hybridisation and other tests that may be developed in future for HPV detection. The tonsil samples will also be examined histologically for pre-malignancy to examine the molecular profile and genetic changes within the pre-malignant sample and to compare it to those of the normal tonsil, using immunohistochemical, DNA, mRNA and proteomics techniques.
- 3. The blood samples will be tested for antibodies to the HPV L1, and other HPV antibodies. Also other protein testing may be performed. Samples may undergo other forms of detection for HPV within the blood, such as HPV nucleic acids and HPV virus particles.

8. ADVERSE EVENT REPORTING

The collection and reporting of Adverse Events (AEs) will be in accordance with the Research Governance Framework for Health and Social Care and the requirements of the National Research Ethics Service (NRES). Definitions of different types of AE are listed in Appendix 1. The investigator should assess the seriousness and causality (relatedness) of all AEs experienced by the patient with reference to the protocol.

8.1. REPORTING REQUIREMENTS

Investigators should only report AEs that meet the definition of an SAE (see Appendix 1 for definition) and which are thought to be related to the patients' participation in the OROMOUTH study.

8.1.1.1. EXPECTED SERIOUS ADVERSE EVENTS

We are not expecting any SAEs to occur as a result of participation in this non-interventional study thus all SAEs reported will be categorised as unexpected.

8.1.2. REPORTING PERIOD

Details of all SAEs will be documented and reported on the day of sample collection.

8.2. REPORTING PROCEDURE

AEs defined as serious and related to the OROMOUTH protocol should be reported on an SAE Form. When completing the form, the investigator will be asked to define the causality and the severity of the AE which should be documented using the CTCAE version 4.0.

On becoming aware that a patient has experienced an SAE, the investigator (or delegate) must complete, date and sign an SAE Form. The form should be faxed together with a SAE Fax Cover

Sheet to the OROMOUTH Study Office using one of the numbers listed below as soon as possible and no later than 24 hours after first becoming aware of the event:

To report an SAE, fax the SAE Form with an SAE Fax Cover Sheet to:

[name] or [name]

On receipt the OROMOUTH Study Office will allocate each SAE a unique reference number. This number will be transcribed onto the SAE Fax Cover Sheet which will then be faxed back to the site as proof of receipt. If confirmation of receipt is not received within 1 working day please contact the OROMOUTH Study Office. The SAE reference number should be quoted on all correspondence and follow-up reports regarding the SAE. The SAE Fax Cover Sheet completed by the OROMOUTH Study Office should be filed with the SAE Form in the ISF.

For SAE Forms completed by someone other than the investigator the investigator will be required to countersign the original SAE Form to confirm agreement with the causality and severity assessments. The form should then be returned to the OROMOUTH Study Office in the post and a copy kept in the ISF. Investigators should also report SAEs to their own Trust in accordance with local practice.

8.2.1. STUDY OFFICE

On receipt of an SAE Form seriousness and causality will be determined independently by the Clinical Coordinator. An SAE judged by the Investigator or Clinical Coordinator to have a reasonable causal relationship with the sample collection will be regarded as a related SAE.

8.3. REPORTING TO THE RESEARCH ETHICS COMMITTEE

8.3.1. UNEXPECTED AND RELATED SERIOUS ADVERSE EVENTS

The OROMOUTH Study Office will report all events categorised as Unexpected and Related SAEs to the Research Ethics Committee (REC) within 15 days.

8.3.2. OTHER SAFETY ISSUES IDENTIFIED DURING THE COURSE OF THE STUDY

The REC will be notified immediately if a significant safety issue is identified during the course of the study.

8.4. REPORTING TO INVESTIGATORS

Details of all Unexpected and Related SAEs and any other safety issue which arises during the course of the study will be reported to Principal Investigators. A copy of any such correspondence should be filed in the ISF.

9. DATA HANDLING AND RECORD KEEPING

9.1. DATA COLLECTION

The Case Report Form (CRF) will comprise of the forms listed in Table 4.

Table 4: OROMOUTH Case Report Form

Form	Summary of data recorded	Schedule for submission	
	•		

Registration Form	RNO, Initials, Date of Birth, eligibility checklist: confirmation of eligibility	Emailed or faxed as soon as possible after registration		
Baseline Form	Details of HPV vaccination history and demographic information	By post/courier within 2 weeks		
Patient Details Form	Patient address and personal information	By post/courier within 2 weeks		
Sample Data Form	Information on samples collected	By post/courier within 2 weeks		
Second Sample Data Form	Sample collected 3 – 6 months after surgery	By post/courier within 2 weeks		
Discontinuation Form	Information regarding discontinued patients	Immediately upon patients' discontinuation		
Serious Adverse Event Form	See Section 8	Immediately (no later than 24 hours) after first discovering that the patient has experienced an SAE		

The CRF must be completed, signed/dated and returned to the OROMOUTH Study Office by the investigator or an authorised member of the site research team (as delegated on the SSDL) within the timeframe listed above.

Entries on the CRF should be made in ballpoint pen, in blue or black ink, and must be legible. Any errors should be crossed out with a single stroke, the correction inserted and the change initialled and dated. If it is not obvious why a change has been made, an explanation should be written next to the change. Refer to the General Paper CRF Completion Guidelines for more information.

Data reported on each form should be consistent with the source data or the discrepancies should be explained. If information is not known, this must be clearly indicated on the form. All missing and ambiguous data will be queried. All sections are to be completed before returning.

In all cases it remains the responsibility of the investigator to ensure that the CRF has been completed correctly and that the data are accurate.

On completion, the top copy of each form must be submitted to the OROMOUTH Study Office and the bottom copy filed in the ISF.

Study forms may be amended by the OROMOUTH Study Office, as appropriate, throughout the duration of the Study. Whilst this will not constitute a protocol amendment, new versions of the form must be implemented by participating sites immediately on receipt.

9.2. ARCHIVING

It is the responsibility of the Principal Investigator to ensure all essential study documentation and source records (e.g. signed Informed Consent Forms, ISFs, patients' hospital notes, copies of CRFs etc.) at their site are securely retained for at least 10 years after the end of the study. Do not destroy any documents without prior approval from the CRCTU Document Storage Manager.

10. QUALITY MANAGEMENT

OROMOUTH study will be coordinated by the CRCTU and InHANSE at the University of Birmingham according to the current guidelines for Good Clinical Practice (GCP).

10.1. SITE SET-UP AND INITIATION

All sites will be required to sign a Clinical Study Site Agreement prior to participation. In addition all participating Investigators will be asked to sign the necessary agreements and supply a current CV to the OROMOUTH Study Office. All members of the site research team will also be required to sign the SSDL, which should be returned to the OROMOUTH Study Office. Prior to commencing recruitment all sites will undergo a process of initiation. Key members of the site research team will be required to attend either a meeting covering aspects of the study design, protocol procedures, Sample collection and reporting of data and record keeping. Sites will be provided with an ISF containing essential documentation, instructions, and other documentation required for the conduct of the study. The OROMOUTH Study Office must be informed immediately of any change in the site research team.

10.2. CENTRAL MONITORING

Where a patient has given explicit consent/assent, sites are requested to send in copies of signed Informed Consent Forms/Assent Forms for in-house review.

Research staff will be in regular contact with the site research team to check on progress and address any queries that they may have. Research staff will check incoming CRFs for compliance with the protocol, data consistency, missing data and timing. Sites will be sent Data Clarification Forms (DCFs) requesting missing data or clarification of inconsistencies or discrepancies.

Sites may be suspended from further recruitment in the event of serious and persistent non-compliance with the protocol and/or GCP, and/or poor recruitment. Any major problems identified during monitoring may be reported to Trial Steering Committee (TSC) and the relevant regulatory bodies. This includes reporting serious breaches of GCP and/or the study protocol to the Research Ethics Committee (REC).

10.3. AUDIT AND INSPECTION

The Investigator will permit study-related monitoring, audits, ethical review, and regulatory inspection(s) at their site, providing direct access to source data/documents.

10.4. NOTIFICATION OF SERIOUS BREACHES

Sites are requested to notify the OROMOUTH Study Office of a suspected study-related serious breach of GCP and/or the study protocol. Where the OROMOUTH Study Office is investigating whether or not a serious breach has occurred, sites are also requested to cooperate with the OROMOUTH Study Office in providing sufficient information to report the breach where required and in undertaking any corrective and/or preventive action.

- The conditions and principles of GCP in connection with that study or;
- . The protocol relating to that study, within 7 days of becoming aware of that breach
- For the purposes of this regulation, a "serious breach" is a breach which is likely to effect to a significant degree:
 - The safety or physical or mental integrity of the patients of the study; or
 - The scientific value of the study

11. END OF STUDY DEFINITION

The end of study will be the date of last visit of the last patient recruited. The OROMOUTH Study Office will notify the REC that the study has ended and a summary of the clinical study report will be provided within 12 months of the end of the study.

12. STATISTICAL CONSIDERATIONS

12.1. DEFINITION OF OUTCOME MEASURE

See section 2.2.1 and 2.2.2.

12.2. ANALYSIS OF OUTCOME MEASURE

The statistical analyses will be described in detail in a statistical analysis plan (SAP). All of the tests will be two-sided with an alpha level of 0.05.

12.2.1. PRIMARY OUTCOME:

The overall prevalence will be estimated as the number of patients with HPV detected in tonsils divided by the total number of patients with available samples. An exact 95% confidence interval will be computed. The prevalence per age and gender group will be calculated similarly.

The relationship between prevalence and age will be explored using logistic regression with the age as a continuous covariate and gender and centre as categorical covariate. The number of degrees (one, two, three) of the model and possible variable transformation (e.g. log-transformation of age) could be determine based on graphical analysis of prevalence versus age relationship and on model fit criteria (e.g. AIC).

12.2.2. SECONDARY OUTCOME:

The overall prevalence will be estimated as the number of patients with HPV detected in oral fluid, oropharyngeal scrapes and urine samples divided by the total number of patients with available samples. An exact 95% confidence interval will be computed.

The prevalence per age and gender group will be calculated similarly. Prevalence rate will be compared among centres using a Cochran-Mantel-Haenszel test with stratification by age group.

Relationship between the prevalence of HPV in tonsils and the prevalence of HPV in oropharyngeal scrapes, oral fluid, and urine samples will be analysed by computing kappa coefficient. Specificity, sensitivity, positive predictive value and negative predictive value of HPV detection in the different sample types will be derived using the oral sample results as the reference.

Relationship between presence of anti-HPV L1 antibody in oral fluid samples and occurrence of HPV in tonsils and/or in oropharyngeal scrape samples will be analysed by computing kappa coefficiency. Specificity, sensitivity, positive predictive value and negative predictive value of anti-HPV L1 antibody assay will be derived using the oral sample results as the reference.

The rate of HPV persistence will be calculated as the proportion of baseline HPV-positive patients who again test HPV-positive in oral fluid, fingertip/nail brushings and urine samples collected after approximately 3 - 6 months. The rate of oral HPV infection clearance will be calculated as the proportion of baseline HPV-positive patients who test HPV-negative in oral fluid, fingertip/nail brushings and urine samples collected after approximately 3 - 6 months.

HPV incidence will be calculated as the proportion of baseline HPV-negative patients who test HPV positive in oral fluid, fingertip/nail brushings and urine samples collected after approximately 3 - 6 months. Exact 95% confidence intervals will be computed.

Multi variable regression models will be used to calculate the odds ratios of different risk factors for having HPV DNA in the tonsil and in the oropharynx, Variables to be included in the model (e.g. serological markers and clinical risk factors such as HPV vaccination status, tobacco and alcohol use) will be selected on the basis of descriptive statistics/possible causal relationship and/or a stepwise approach. Analysis of results may be performed to identify a possible marker or combination of markers for screening for persistent HPV infections in the oropharynx.

Among females in the target age class for vaccination (12 to 24 years), exploratory analyses will compare the HPV prevalence rate in HPV vaccinated and non HPV vaccinated patients using a Fisher's exact test. Association between HPV vaccine and oral HPV infection will be assessed using a case-control approach. Cases will be patients with HPV positive oral sample and controls will be patients with HPV negative oral sample. The exposure to vaccine will be compared between the case and the control groups using logistic regression, OR and its 95% confidence interval will be derived.

Prevalence of HPV in tonsils will be described and compared between the current cohort and the comparison historical cohort using a Cochran-Mantel-Haenszel test with stratification by age group and gender.

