2.1. OBJECTIVES

2.1.1. PRIMARY OBJECTIVE:

• To estimate the overall, age and gender specific prevalence of HPV in the oropharynx in patients undergoing tonsillectomy for non-malignant conditions

2.1.2. SECONDARY OBJECTIVES:

- To compare the HPV oropharynx prevalence between different sites—in order to identify the different reservoirs of HPV infection
- To describe the distribution of HPV seropositivity in the study population by age and gender
- To describe HPV-type distribution overall by age, gender, and sampling site
- To describe distribution by age and gender of patients who are both HPV PCR positive and anti-HPV L1 sero-positive – predicting persistent HPV infection
- To provide preliminary estimates of the clearance and persistence of HPV infection and antibodies in the oropharynx, as detected in follow-up oral fluid, finger tips/nail brushings and urine samples
- To assess the presence of anti-L1 HPV antibodies in saliva as a marker of vaccination or previous infection in the oral cavity
- To assess the presence of HPV in the urine
- To assess the presence of HPV in finger tips/nail brushings
- To provide preliminary evaluation of the performance of potential non-invasive tests for the detection of HPV infection in the mouth against HPV detection rates in tonsillectomy and oropharyngeal scrapes
- To identify the change in overall prevalence and distribution of HPV in tonsils over time, and to describe preliminary data on age and gender specific changes over time
- To provide preliminary data on the potential effect of HPV vaccination in the prevention of oral infection

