12.3. SAMPLE SIZE CONSIDERATIONS

An analysis of current literature suggests that in a population recruited between 1990 and 2000, the prevalence of oral HPV was about 6.5%, varying from 0% - 10%. However, in an analysis of oropharyngeal scrapes and oral washings, the prevalence of HPV detection was much higher at 31%.

Pilot data of patients having tonsillectomy at University Hospital Coventry over two 3-month time periods are shown below in table 3. The number of tonsillectomy operations performed at the Heart of England NHS Foundation Trust - is approximately 50% of that for University Hospital Coventry quoted below.

Table 5: The number of tonsillectomy operations performed at University Hospital Coventry.

Age Group*	Number of Monthly recruitment (%)		
0-4	7 (12%)		
5-9	12 (20%)		
10-14	7 (12%)		
15-19	10 (17%)		
20-24	6 (10%)		
25-29	5 (8%		
30-34	4 (7%)		
35-39	5 (8%)		
40-44	1 (2%)		
45-49	1 (2%)		
50-69	1 (2%)		
Total	59		

^{*}There was an equal distribution of males and females in the group.

We plan to enrol 925 patients. The precision of the overall prevalence estimate that would be achieved with such a number is summarised in Figure 1 for prevalence ranging from 1 to 31 %. For example, if the observed prevalence is 10 %, the 95 % confidence interval for the overall population will be 8.4 to 11.8 % corresponding to a relative precision of 17 %.

[figure not shown]

Figure 1: Precision (95% confidence interval) of the prevalence estimate versus the prevalence observed in a random sample of 1250 patients.

We will also undertake a stratified sampling strategy to allow comparisons between those aged 14 and under (non-exposed, approximately one third of the cohort), and patients over 14 years of age (exposed) to allow the determination of the age of acquisition of infection and the optimal age of start of vaccination. The stratified sampling strategy will recruit patient subgroups as follows:

Table 6: The stratified sampling strategy for patient recruitment.

Age group	Sample size (%)		
0-4	150 (16.5%)		
5-9	150 (16.5%)		
10-14	150 (16.5%)		
15-19	150 (16.5%)		
20-24	150 (16.5%)		
25-34	100 (11%)		
35-44	60 (5.5%)		
45-65	15 (1.0%)		
Total	925		

[figure not shown]

Figure 2: Precision (95% confidence interval) of the prevalence estimate versus the prevalence observed in a random sample of 100, 150, and 250 patients.

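### Overall prevalence is defined as an unweighted proportion from an age-quota sample, so it describes the quota mix rather than the tonsillectomy population unless prevalence is unrelated to age

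*Protocol*

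**What the plan says.** The primary objective (Protocol Section 2.1.1) is "To estimate the overall, age and gender specific prevalence of HPV in the oropharynx in patients undergoing tonsillectomy for non-malignant conditions". The target is therefore the population having this operation.

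The sample is not drawn in proportion to that population. Section 7, item 8: "Stratified sampling will be employed to ensure that sufficient numbers of patients are recruited from all age groups", with emphasis on ages 10 to 20. Section 12.3: "The stratified sampling strategy will recruit patient subgroups as follows". Table 6 then gives fixed numbers: 150 in each five-year band from 0-4 to 20-24, 100 aged 25-34, 60 aged 35-44 and 15 aged 45-65, in total 925.

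Section 12.2.1 defines the overall estimate as the "number of patients with HPV detected in tonsils divided by the total number of patients with available samples" and adds: "An exact 95% confidence interval will be computed". Section 12.2.2 uses the same definition for oral fluid, scrapes and urine. The protocol mentions no weighting or age standardisation. Section 12.3 attaches the resulting interval to the overall population, and its figure captions describe precision as that of a random sample.

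**The concern.** Pooling all patients without weights gives each age band the weight of its quota. Where the quotas depart from the natural age mix and prevalence changes with age, the pooled figure answers a different question from the one in the objective. The simple binomial interval is then centred on the quota-mix value.

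The protocol itself expects prevalence to change with age. Section 12.3 treats patients aged 14 and under as non-exposed and older patients as exposed, and aims to find the age of acquisition. Section 12.2.1 plans to model prevalence on age. The literature it tabulates shows gradients: one oral series in Table 1 reports 8.7% under 7 years, 0% at 7-12 and 5.2% at 13-20, and the footnote to Table 2 mentions a fall from 11.5% in preschool children to 0% in older adults.

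At stake is the headline overall estimate, which is meant to inform vaccination policy, and the matching overall figures for the secondary specimens.

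**Working it through.** **Inputs.** Quotas n by band (Table 6): 150, 150, 150, 150, 150, 100, 60, 15; total 925 ("We plan to enrol 925 patients"). Natural mix t (Table 5, "The number of tonsillectomy operations performed at University Hospital Coventry", monthly), merged to the same bands: 7, 12, 7, 10, 6, 5+4=9, 5+1=6, 1+1=2; total 59.

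**The plan's own precision figure.** Section 12.3 gives 8.4 to 11.8% at an observed 10%, relative precision 17%. The exact (Clopper-Pearson) interval is 8.1 to 12.1% with n=925 (relative half-width 20%) and 8.39 to 11.80% with n=1250 (17.0%). The printed figure therefore belongs to 1250 patients, the number in the Figure 1 caption.

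**Quota share against natural share.**

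| Age | n/925 | t/59 | Ratio |
|---|---|---|---|
| 0-4 | 16.2% | 11.9% | 1.37 |
| 5-9 | 16.2% | 20.3% | 0.80 |
| 10-14 | 16.2% | 11.9% | 1.37 |
| 15-19 | 16.2% | 16.9% | 0.96 |
| 20-24 | 16.2% | 10.2% | 1.59 |
| 25-34 | 10.8% | 15.3% | 0.71 |
| 35-44 | 6.5% | 10.2% | 0.64 |
| 45+ | 1.6% | 3.4% | 0.48 |

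**Size of the shift.** With age-specific prevalence p and W = t/59:

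- crude = Σ n·p / 925
- weighted = Σ W·p
- variance ratio = [Σ W²·p(1-p)/n] / [crude(1-crude)/925]

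The protocol gives no age curve for this population, so the curves below are assumptions. Worked example, 2% under 25 and 10% from 25: crude = (750×2 + 175×10)/925 = 3.51%; weighted = (42×2 + 17×10)/59 = 4.31%. Exact intervals use the expected counts.

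| Assumed curve | Crude (exact 95% CI) | Weighted | Shift, points (relative) | Variance ratio |
|---|---|---|---|---|
| Flat 6.5% | 6.5 (5.0-8.3) | 6.5 | 0 | 1.12 |
| 1% under 15, 5% at 15-24, 8% at 25+ | 3.6 (2.5-5.0) | 4.1 | -0.48 (-12%) | 1.39 |
| 2% under 25, 10% at 25+ | 3.5 (2.4-4.9) | 4.3 | -0.79 (-18%) | 1.57 |
| 2% under 15, 5% at 15-24, 15% at 25+ | 5.4 (4.1-7.1) | 6.6 | -1.13 (-17%) | 1.49 |
| 2% under 15, 10% at 15+ | 6.1 (4.7-7.9) | 6.5 | -0.37 (-6%) | 1.22 |
| 2% at 0-9, 10% at 10-24, 3% at 25+ | 6.1 (4.6-7.8) | 5.4 | +0.67 (+12%) | 0.86 |
| Falling by band: 11.5, 8, 5, 3, 2, 1, 0, 0% | 4.9 (3.6-6.5) | 4.5 | +0.44 (+10%) | 0.87 |

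In every row the weighted value lies inside the crude interval. It falls outside only under extreme curves, such as 31% in one age range and 1% elsewhere: 6.7% (5.2-8.5) against 9.6% if the range is 25+, and 15.6% (13.3-18.1) against 12.7% if it is 10-24.

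**Cost of weighting when prevalence is flat.** 925 × Σ W²/n = 1.12, an effective sample size of about 925/1.115 = 829.

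**The case against.** Several counter-arguments carry weight.

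- **Much of the primary objective is untouched.** Prevalence by age group with exact intervals and the logistic model on age do not depend on the quota mix across bands. The historical comparison is age- and sex-matched and tested with stratification by age group and gender. Published age-band results would let a reader re-weight. This stands and limits the point to the pooled figures.
- **Table 5 is a weak stand-in for the population.** It covers one hospital, about 59 operations a month, with mostly single-digit cells and a top band reaching 69 although eligibility ends at 65. The study is multi-centre. This stands: Table 5 shows that the quotas depart from a natural mix, but it is not a sound main source of weights.
- **Weighting can cost more than it gains.** With flat prevalence the error is 0.81 points crude and 0.86 weighted. With the 2%/10% step at age 15, root mean squared error is about equal (0.87 each). With 2%/10% split at 25, weighting wins (crude √(0.79²+0.61²) = 1.00 against 0.76).
- **The SAP may add standardisation.** It may, but the protocol states the crude estimator outright, so the SAP would be supplementing or departing from it.

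A reader might also set these shifts beside the 17% relative precision in Section 12.3 and conclude that the bias is as large as the sampling error. The documents do not support that. The 17% applies at 10% prevalence and reproduces only with 1250 patients. At about 3.5% prevalence with 925 patients the relative half-width is about 35%, so the -18% case is 0.79/1.25 = 0.64 of the half-width and the -12% case is 0.48/1.26 = 0.38.

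**Conclusion.** The mismatch is real. The protocol fixes both disproportionate age quotas and an unweighted overall estimator, and the two together do not estimate the population in the primary objective unless prevalence is unrelated to age or the differences cancel. Under the assumed moderate curves the shift is zero to about 1.1 percentage points, roughly -18% to +12% relative. The shift can go either way, and in each of these cases it lies within the crude 95% interval. These sizes rest on assumed age curves and on Table 5 as a proxy for the tonsillectomy mix.

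The wording should be corrected, but the point does not undermine the study. A reader might infer that the primary result is invalid or biased in a known direction. The documents support neither: the age curve is unknown, and the age-specific results and the age-stratified historical comparison are largely unaffected.

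**What to change.** In Sections 12.2.1 and 12.2.2:

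- Define overall and sex-specific prevalence as the sum of age-stratum prevalences, weighted to the age mix of all eligible tonsillectomies at the participating sites.
- Take the weights from the hospital operation lists already used to identify patients (Section 5). The log of patients approached is less suitable, because it may reflect the quotas once strata fill. Use Table 5 only as a sensitivity source.
- Use a confidence interval built for a stratified, weighted proportion, and state in advance how the sparse 45-65 stratum (15 patients) is handled.
- Keep exact intervals for single age strata.
- Report the crude figure alongside, labelled as the sample proportion.

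The cost is analysis wording plus an age tabulation of existing lists. The statistical price is a variance ratio of about 1.1 if prevalence is flat and about 0.9 to 1.6 across the assumed curves. The higher values occur where prevalence is concentrated in the under-sampled older bands, which is also where the crude figure is furthest off.
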